#### 5.4. *Body Impedance Analysis*

The BIA technique is based on the fact that lean tissues have a high water and electrolyte content, and thus provide a good electrical pathway. Fat contains a lower percentage of body water, and thus is a poor conductor of the electrical signal. Utilizing a low energy, high frequency, electrical signal (50 kHz, 500 micro amp), a measurement of the baseline resistance and reactance to the flow of electrical current can be made. The measurement relates directly to the volume of the conductor, which is used to determine total body water, lean body mass, and finally, fat mass and percent body fat measurement on the Tanita® scale.

#### 5.5. *Telomere length*

Telomere length will be measured in genomic DNA extracted from stored buffy coat samples by quantitative polymerase chain reaction (qPCR) using a method adapted from the one originally described by Cawthon (2009). Telomere length will be performed on the blood samples collected before the dietary intervention and at the end of the two treatments (visit 2, month 6)(see Table 1). Telomere length measurements will be carried out at the laboratory of Genetics of Department of Biology, Ecology and Earth Sciences, University of Calabria.

#### 5.6. *Clinical and Research Laboratory Evaluations and Specimen Collection*

##### *5.6.1. Biohazard Containment*

As the transmission of HIV and other blood-borne pathogens can occur through contact with contaminated needles, blood, and blood products; appropriate blood and secretion precautions will be employed by all personnel in the drawing of blood and shipping and handling of all specimens for this study, as currently recommended by the Centers for Disease Control and Prevention and the National Institutes of Health.

## 6. **Safety**

### *6.1. Definition of an Adverse Event (AE)*

An AE is any unanticipated or unintended medical occurrence or worsening of a sign or symptom (including an abnormal laboratory finding) or disease in a study subject, including those events which do not necessarily have a causal relationship with the study condition, procedures or Study Product(s), that occurs after the informed consent is obtained.

Pre-existing conditions or illnesses which are expected to exacerbate or worsen are not considered adverse events and will be accounted for in the subject's medical history.

### *6.2. Definition of a Serious Adverse Event (SAE)*

A SAE is defined as an AE meeting one of the following outcomes:

- Death during the period of protocol defined surveillance.

- Life Threatening Event (defined as a subject at immediate risk of death at the time of the event).
- Inpatient hospitalization or prolongation of existing hospitalization during the period of protocol defined surveillance.
- A congenital anomaly or birth defect
- A persistent or significant disability/incapacity.
- Any other important medical event that may not result in one of the above outcomes, may be considered a serious adverse event when, based upon appropriate medical judgment, the event may jeopardize the subject and may require medical or surgical intervention to prevent one of the outcomes listed above. Examples of such medical events include allergic bronchospasm requiring intensive treatment in an emergency room or at home, blood dyscrasias or convulsions that do not result in inpatient hospitalization, or the development of drug dependency or drug abuse.

### 6.3. *Assessing, Recording, Analyzing, and Managing Safety Parameters*

#### 6.3.1. *Methods and Timing for Assessment*

Adverse or clinical events will be assessed at each clinical visit. Each visit is conducted by a clinician. All reported events will be recorded in the subject's medical record.

#### 6.3.2. *AE Severity — Grading Scale*

Each adverse event will be graded for severity. All laboratory and clinical AEs that occur in a subject, will be assessed for severity and classified into one the categories below following a standard criterion of Mild, Moderate or Severe.

- Mild Adverse Event — event requires minimal or no treatment and does not interfere with the subject's daily activities.
- Moderate Adverse Event — event results in a low level of inconvenience or concern with the therapeutic measures. Moderate events may cause some interference with functioning.
- Severe Adverse Event — event interrupts a subject's usual daily activity and may require systemic drug therapy or other treatment. Severe events are usually incapacitating.

#### 6.3.3. *AE/SAE Causality — Relatedness Scale*

For all collected AEs, the clinician who examines and evaluates the subject will determine the adverse event's causality based on temporal relationship and his/her clinical judgment. The degree of certainty about causality will be graded using the categories below:

- Definitely Related: There is clear evidence to suggest a causal relationship, and other possible contributing factors can be ruled out. The clinical event, including an abnormal laboratory test result, occurs in a plausible time relationship to study product administration and cannot be explained by concurrent disease or other drugs or chemicals. The response to withdrawal of the product (de-challenge) should be clinically plausible. The event must be pharmacologically or phenomenologically definitive, with use of a satisfactory re-challenge procedure if necessary.
- Possibly Related: there is some evidence to suggest a causal relationship (e.g., the event occurred within a reasonable time after administration of the study product). However, the influence of other factors may have contributed to the event (e.g., the subject's clinical condition, other concomitant events). Although an adverse event may rate only as "possibly related" soon after discovery, it can be flagged as requiring more information and later be upgraded to as appropriate.

- Unlikely: a clinical event, including an abnormal laboratory test result, whose temporal relationship to the study product makes a causal relationship improbable (e.g., the event did not occur within a reasonable time after administration of the study product) and in which other drugs or chemicals or underlying diseases provide plausible explanations (e.g., the subject's clinical condition, other concomitant treatments).
- Unrelated/None: the AE is completely independent of study product administration, and/or evidence exists that the event is definitely related to another etiology. There must be an alternative, definitive etiology documented by the clinician.
- Expected Events Related to Disease Process: expectedness refers to the awareness of adverse events previously observed, not on the basis of what might be anticipated from the pharmacological properties of the Study Product.

#### *6.3.4. Recording/Documentation*

At each contact with the subject, information regarding adverse events will be elicited by appropriate questioning and examinations and will be immediately recorded on a source document. Source documents will include: progress notes, laboratory reports, consult notes, phone call summaries, survey tools and data collection tools. Source documents will be reviewed in a timely manner by the research team. All reportable adverse events that are identified will be recorded on an appropriate case report form (CRF) if applicable. The start date, the stop date, the severity of each reportable event, and the PI's judgment of the AEs relationship to the Study Product/intervention will also be recorded in the Subject's progress notes or on the CRF if applicable.

#### *6.3.5. Specific Serious Adverse Event Requirements*

SAEs will be handled according to good clinical practices associated with Serious Adverse Events. SAEs will be recorded in the study's SAE form and clinician progress notes, and require expeditious handling and reporting to the Sponsor.

Follow-up information which becomes available as the SAE evolves, as well as supporting documentation, will be collected subsequently and reported to the Sponsor. The PI will report SAE events to the IRB if applicable, in compliance with IRB requirements.

#### *6.3.6. Reporting of Pregnancy*

Should a woman become pregnant or suspects she is pregnant while participating in this study, she is instructed to inform study staff and her primary care provider immediately.

### *6.4. Type and Duration of the Follow-up of Subjects after Adverse Events*

#### *6.4.1. Monitoring of Subjects*

At each contact with the subject, the investigator must seek information on adverse events by specific questioning and, as appropriate, by examination.

AEs may be observed by the Investigator and/or study staff, elicited from the subject and/or family member, or volunteered by the study subject. Adverse events that had previously been reported by study subject will

also be reassessed for duration, intensity and possible reoccurrence. Assessment of safety will include clinical observation and monitoring of hematological, chemical, and immunologic parameters.

Any AE that occurs between the times a study Subject signs the informed consent form and the time s/he departs the study at the end of the final visit (or at the time of early discontinuation of the subject from the study for any reason) will be captured and recorded.

Due to the nature and composition of the study product, no delayed toxicities or withdrawal effects are expected after a subject has discontinued participation in the study. Therefore, no collection of safety information will be done after subject's discontinuation from the study granted that the subject does not have any unresolved AEs.

#### *6.4.2. Follow-up of Subjects after Adverse Events*

All SAEs and non-serious AEs reported in this study will be followed until resolution or until the investigator and the clinical/medical monitor are in agreement that the AE/SAE has stabilized and no more follow-up is required. This requirement indicates that follow-up may be required for some events after the patient discontinues participation from the study.

#### *6.4.3. Modification of Study Product(s)/Intervention(s) for a Subject*

No food substitutes are permitted. A reduction of food products, a hold of food or discontinuation of food product is allowed at the discretion of the study clinician.

#### *6.4.4. Halting Rules for the Protocol*

The PI will closely monitor and analyze study data as it becomes available and will make determinations regarding the presence and grading of adverse events. Evaluation of adverse events will be analyzed for the study products and with regard to the known complications associated with administration. The study will be halted (no new enrollments and no further administration of product) by the investigators and a report will be submitted to the IRB (if applicable) if a safety issue is identified.

#### *6.4.5. Stopping Rules for an Individual Subject*

A study subject will be discontinued from further Study Product(s) administration for:

a significant reduction of BMI greater than 15% from baseline measurement and in any case of a BMI measurement lower than 22 Kg/m^2 for women and 23 Kg/m^2 for men during the follow-up visits; any clinical adverse event, laboratory abnormality, concurrent illness, other medical condition.

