Efficacy assessments	
Primary objectives: linear mixed models will be used to compare arm 1 (FMD) and arm 2 (FMD+LD) to the arm 3 (control group) sitting fat mass expressed in terms of change from baseline to the visit 3.
 
Secondary objectives: linear mixed models will be used to compare FMD+LD and FMD to the control group sitting the following parameters expressed in terms of change from baseline to the visit 3: inflammatory biomarkers, IGF-1, blood pressure, serum lipids, glucose, CV biomarkers, body weight, BMI, body composition, insulin resistance, and aging biomarkers, proportion of participants who receive antihypertensive/hypoglycemic medications, sleep quality and duration.

Key safety assessments	AEs and AEs leading to discontinuation
Key words	Longevity Diet, Fasting Mimicking Diet, Body Composition

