### 3.1. Selection and withdrawal of subjects

#### 3.1.1. Inclusion Criteria

- Subjects of 30-65 years of age;
- Body mass index equal to or greater than 25 kg/m^2.  
And at least one of the following:
- obesity (Body mass index equal to or greater than 30 kg/m^2).
- HbA1C greater than 5.6% (38 mmol/mol);
- IGF-1 level greater than 200 ngml;
- systolic blood pressure >130 mmHg and diastolic blood pressure >90 mmHg; the inclusion of individuals currently taking antihypertensive medications is allowed. In this last case a careful attention will have to be paid to the self-monitoring of blood pressure during the FMD cycles;
- triglycerides >150 mgdl;
- C-reactive protein >1 mgL;

- total cholesterol >190 mgdL and LDL cholesterol >129 mgdL.

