### *6.8. Study Discontinuation*

The study will be discontinued for the following reasons:

- any clinical adverse event or serious adverse event, laboratory abnormality or inter-current illness which, in the opinion of the PI, indicates the continued treatment with study therapy is not in the best interest of the subjects.
- Termination of the study by the Sponsor.

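### Section 6.4.5 makes any adverse event, illness or other medical condition a compulsory stop of study product, without qualifier, and is not reconciled with sections 6.4.3, 3.5 and 3.6

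*Protocol*

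**What the plan says.** Section 6.4.5 of the protocol (individual stopping rules) states that a subject "will be discontinued from further Study Product(s) administration" on either of two limbs. The first is a set of BMI limits. The second is "any clinical adverse event, laboratory abnormality, concurrent illness, other medical condition", and the sentence ends there.

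Other sections bear on the same decision:

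- **Section 6.4.3** (modification of product): "A reduction of food products, a hold of food or discontinuation of food product is allowed at the discretion of the study clinician".
- **Section 6.1** (AE definition): covers unintended occurrences and abnormal laboratory findings after consent, whether or not they are causally linked to the product.
- **Section 6.3.2** (grading): a mild event is one where the "event requires minimal or no treatment and does not interfere with" daily activities.
- **Section 3.5**: medication may be started in the study when it is prescribed for a specific clinical event.
- **Section 3.6**: acetaminophen may be used for mild headache or myalgia.
- **Section 6.8** (stopping the whole study): lists nearly the same triggers, but only those "which, in the opinion of the PI, indicates the continued treatment with study therapy is not in the best interest of the subjects".
- **Protocol Summary**, key safety assessments: "AEs and AEs leading to discontinuation".

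**The concern.** The rule in 6.4.5 is compulsory and its trigger list is open-ended. Read with the protocol's own definitions, a mild cold unrelated to the diet is enough to end FMD administration for that subject. The judgement clause that would prevent this appears in 6.8 for the whole study, but not in 6.4.5 for one subject, and no other section supplies it there.

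Two things are at stake. The first is exposure to the assigned diet in arms 1 and 2. The second is the meaning of a key safety assessment: if every event compels a stop, counting events that led to a stop says little beyond counting events. If clinicians instead use the discretion in 6.4.3, they depart from the letter of 6.4.5, and two clinicians may handle the same event differently while each can point to the protocol.

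**Working it through.** **1. How wide is the trigger?** Take a mild headache during an FMD cycle and read it through each section.

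| Section | Consequence |
|---|---|
| 6.1 | It is an unintended medical occurrence after consent, so it is an AE whatever its cause |
| 6.3.2 | Mild |
| 3.6 | Acetaminophen may be given |
| 6.4.3 | The clinician may reduce, hold or stop product, and need do none of these |
| 6.4.5 | Product must be stopped |

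Sections 3.6 and 6.4.3 both contemplate a subject who carries on. Section 6.4.5 leaves one outcome. The conflict is limited to the triggers that 6.4.5 lists; 6.4.3 still operates for other reasons, such as tolerability or preference.

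**2. Would such events come to light while product remains to be given?** Yes. Under section 3.3, subjects in arms 1 and 2 are telephoned at the end of each FMD cycle (day 6) and every 2 months, and are asked about signs and symptoms of adverse events. Minor events after cycles 1 and 2 will therefore be elicited.

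**3. Does the laboratory limb add much?** Little. Table 1 in section 3.3 schedules haematological analyses at screening, baseline and visit 3, and not at visit 2. Section 3.3.4 agrees. Visit 3 comes 5-7 days after the third cycle (section 3.3.5), when no product is left to stop. Between the first box and visit 3, only an unscheduled test or self-monitoring could meet this limb.

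**4. Exposure lost by one stopped subject.** Inputs: 3 FMD cycles (section 7.7.1; one box at baseline plus 2 more in section 4.1.1) and 5 days per cycle (section 3).

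- Planned FMD days: 3 × 5 = 15.
- Stopped after cycle 1: 2 × 5 = 10 days lost; 10/15 = 67%.
- Stopped after cycle 2: 1 × 5 = 5 days lost; 5/15 = 33%.
- Stopped after cycle 3: 0 days lost.

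A stop part-way through a cycle also loses the rest of that cycle.

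**5. Whom the rule can reach.** Arms 1 and 2 receive FMD boxes: 167 + 167 = 334 of 501 subjects (334/501 = 67%). Arm 3 receives no product, so nothing can be stopped there. An arm 2 subject taken off the boxes could still follow the Longevity Diet.

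**6. Effect on the trial.** To go from step 4 to an average loss of exposure, one needs the proportion of subjects with an event before cycle 2 and before cycle 3. The protocol gives no AE rate, so the calculation stops here.

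**The case against.** The strongest reply is that nobody would run the trial this way. The protocol grades severity and relatedness, provides rescue medication, and has the PI-opinion clause in 6.8, so the intended meaning is fairly clear and the literal scenario is unlikely. The rule also errs toward subject safety. Severity and relatedness are recorded for each event in any case, so safety information is not lost. All of this stands as a reason to call the point minor. It does not supply the missing clause: sensible conduct would still depart from the written rule.

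A second reply is that 6.4.3 is permissive and lists discontinuation among its options, so a clinician who stops product under 6.4.5 breaches nothing in 6.4.3. That is right, and it is why the two sections are described as unreconciled rather than flatly contradictory.

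A reader might also infer more than the text supports:

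- **That subjects meet the stopping rule from entry**, because an HbA1c above 5.6% can itself be the qualifying abnormality (section 3.1.1). A rule about further administration is naturally read as addressing findings after entry, and no blood panel is scheduled between the first box and visit 3.
- **That different sites would diverge.** The protocol speaks of dispensing at the study site (section 4.1.1); any divergence would be between clinicians.
- **That the safety assessment fails across the trial.** AEs are collected in all arms up to the final visit, arm 3 has no product to stop, and events after the last cycle cannot stop any.

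**Conclusion.** The concern holds as a drafting fault in a stated rule. Section 6.4.5 compels a stop of study product for any adverse event, concurrent illness or other medical condition, with no qualifier; the laboratory limb has the same fault but little practical reach. Followed literally, a subject in arm 1 or 2 would lose 10 of 15 FMD days if stopped after cycle 1 and 5 of 15 if stopped after cycle 2. In those arms, before the last cycle, AEs leading to discontinuation would nearly coincide with all AEs.

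These figures describe one stopped subject under literal compliance. They are not an expected effect of the rule. It would be tempting to conclude that power is lost or that the 30% dropout allowance in section 7.4 is too small. The documents do not support either: there is no AE rate, and stopping product is not the same as leaving the study. Severity: minor.

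**What to change.** Amend the second limb of 6.4.5 so that an adverse event, laboratory abnormality, concurrent illness or other medical condition stops product only when, in the opinion of the PI, it shows that continuing study product is not in that subject's best interest. This is the clause of section 6.8 applied to one subject. Add a cross-reference to 6.4.3 for holds and reductions. Leave the BMI limits unchanged.

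The cost is protocol wording only. No visit, assessment or sample size changes, and clinicians remain free to stop product for safety.

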#### *6.4.6. Premature Withdrawal of a Subject*

A subject may decide to withdraw informed consent for any reason. Premature discontinuation by a subject will be evaluated to assess the status of the subject at termination, and will be recorded in the subject's medical record and in the CRF.

#### *6.4.7. Replacement of a Subject Who Discontinues Study Treatment*

Subjects may be replaced at the PI's discretion.

### *6.5. Research Use of Stored Human Samples, Specimens or Data*

#### *6.5.1. Use of Stored Data*

Any other research or experimental treatments will be done under additional protocols for which separate signed informed consent documents will be obtained.

#### *6.5.2. Disposition of Stored Samples and Data*

Data will be stored using codes assigned by the investigators. Data will be kept in password-protected computers. Only authorized members of the study team will have access to the samples and data.

### *6.6. Assent or Informed Consent Process in Case of a Minor*

Minors are excluded from this study.

### *6.7. Subject Confidentiality*

The investigator will ensure that the subject's anonymity is maintained. Subjects will not be identified in any publicly released reports of this study. All records will be kept confidential to the extent provided by federal, state and local law. The study monitors and other authorized representatives of the Sponsor may inspect all documents and records required to be maintained by the Investigator, including but not limited to, medical records.

The investigator will inform the subjects that the above-named representatives will review their study-related records without violating the confidentiality of the subjects. All laboratory specimens, evaluation forms, reports, and other records that leave the site will be identified only by a coded number in order to maintain subject confidentiality. All records will be kept locked and all computer entry and networking programs will be done with coded numbers only. Clinical information will not be released without written permission of the subject, except as necessary for monitoring by the FDA, the Sponsor, or the sponsor's designee.

### *6.8. Study Discontinuation*

The study will be discontinued for the following reasons:

- any clinical adverse event or serious adverse event, laboratory abnormality or inter-current illness which, in the opinion of the PI, indicates the continued treatment with study therapy is not in the best interest of the subjects.
- Termination of the study by the Sponsor.

## **7. Statistical Analysis plan**

### *7.1. Study Randomization*

This is a randomized, open-label three-arm exploratory study. After the screening visit, participants will be randomized through a pre-stratified randomization method to achieve balance between the three groups

(interventions and control group) according to baseline characteristics (covariates) that include gender, age (30-50; 51-65), and BMI (25-29,9; 30 and over) obtaining 8 strata. The block-based randomization will be then performed separately within each layer using a web-based randomisation system (<https://www.project-redcap.org/>) that will be controlled by the researchers not involved in the study from the Valter Longo foundation in Milan.

